**Diet Quality and Genetic Association With Body Mass Index:
Results From Three Observational Studies**

Date of the document: June 01, 2018

Background

In the most recent GWAS, of the 97 BMI-associated SNPs identified, more than half of the SNPs were highly enriched for expression in the central nervous system (CNS), which is the key site of central appetite regulation ¹. Significant interaction between consumption of sugar-sweetened beverages and genetic score in relation to BMI has been found ². However, it is not known whether diet quality could modify the genetic association with BMI. Moreover, identification of subgroup of established SNPs whose association with BMI could be most significantly modified by diet will provide evidence to individualized obesity prevention.

Hypotheses

- SNPs enriched in the CNS (CNS SNPs) were more likely to be associated with food and nutrient intakes featured in AHEI in comparison to SNPs enriched in other tissues (non-CNS SNPs).
- Higher diet quality was related with less pronounced association between genetic score and BMI, particularly the score of CNS SNPs.

Study Population

- 5,730 women in the NHS and 3,434 men in the HPFS who were sampled as controls
- 21,740 women in the WHGS

Exposure

- Dietary quality will be measured by AHEI-2010, AMED, and DASH diet scores. Diet was measured repeatedly in the NHS (1984, 1986, 1990, 1994) and the HPFS (1986, 1990, 1994), and was measured at baseline in the WGHS.
- Based on the most recent GWAS ¹, we will classify the 97 BMI-associated SNPs into CNS SNP (54 SNPs) and non-CNS SNP (43 SNPs). Total, CNS, and non-CNS SNP scores will be calculated.

Outcome

BMI measured after diet assessment with 2-year lag in the NHS and the HPFS and 3-year lag in the WGHS

Statistical analysis

1. The associations of individual SNP with AHEI components at baseline will be examined using linear regression and the results will be presented in Heatmap.
2. The interactions between diet quality scores and genetic scores in relation to BMI will be examined using generalized linear model in the NHS and the HPFS and using linear regression in the WGHS. The genetic scores will include total SNP score, CNS SNP score, and non-CNS SNP score.
3. Two-way stratification analysis will be conducted: the association of diet quality score with BMI will be stratified by genetic score; the association of genetic score with BMI will be stratified by diet quality score.
4. The interactions between AHEI components and genetic scores in relation to BMI will be examined using generalized linear model in the NHS and the HPFS and using linear regression in the WGHS.

Reference

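### The claim that diet modifies the CNS score in particular has no planned test: no CNS versus non-CNS contrast and no common scale

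*Combined protocol and SAP*

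**What the plan says.** The second bullet under Hypotheses states: "Higher diet quality was related with less pronounced association between genetic score and BMI, particularly the score of CNS SNPs". The Background gives a related rationale: "identification of subgroup of established SNPs whose association with BMI could be most significantly modified by diet".

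Under Exposure, the 97 SNPs are divided into 54 CNS and 43 non-CNS SNPs. On the scores themselves the text says only "Total, CNS, and non-CNS SNP scores will be calculated", without weighting or unit. On diet it says "Dietary quality will be measured by AHEI-2010, AMED, and DASH diet scores" and gives none of the three priority.

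Under Statistical analysis:
- Item 1 relates individual SNPs to AHEI components. It serves the first hypothesis and does not involve BMI.
- Item 2 examines diet-by-score interactions on BMI: "The genetic scores will include total SNP score, CNS SNP score, and non-CNS SNP score".
- Item 3 stratifies diet by genetic score and genetic score by diet.
- Item 4 replaces the diet scores by AHEI components: "The interactions between AHEI components and genetic scores in relation to BMI will be examined using generalized linear model".

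**The concern.** A claim that modification is strongest for the CNS score concerns the difference between two interactions. Two separate interaction estimates inform a reader about that difference, but neither one, nor the pair of p-values, tests it. None of items 1 to 4 names the difference, a heterogeneity test, a model holding both scores, or a rule for deciding the clause.

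Even an informal side-by-side reading needs a common unit. A score of 54 SNPs and one of 43 will generally have different spreads, so interactions that are equal per allele need not be equal per SD. With three diet scores unranked, the comparison could also be taken from whichever one shows it best.

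At stake is the CNS-specific half of the second hypothesis, which the Background links to individualized prevention. It could be claimed when diet modifies both SNP sets equally.

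**Working it through.** **What there is to reproduce.** The plan gives no alpha, power, effect size or sample-size calculation. Its only checkable sum is 54 + 43 = 97, which agrees. The rest is illustration under stated assumptions.

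**Assumptions (not in the documents).** Two-sided alpha 0.05; independent CNS and non-CNS interaction estimates; one diet score; one pooled test per genetic score. Let p be the power of the CNS test and d the matching noncentrality: d = 1.435, 1.960, 2.802, 3.242 and 4.286 for p = 0.30, 0.50, 0.80, 0.90 and 0.99.

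**1. Reading the pattern of p-values.** Suppose the clause is taken as supported when CNS is significant and non-CNS is not.
- True interactions equal per SD: both tests have power p, so P(CNS only) = p(1 − p).
- True interactions equal per allele, with equal variance per SNP: the score SD ratio is r = √(54/43) = 1.12. The non-CNS noncentrality is d/r, and P(CNS only) = p × (1 − power at d/r).

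| CNS power | Equal per SD | Equal per allele |
|---|---|---|
| 30% | 21% | 22.5% |
| 50% | 25% | 29.2% |
| 80% | 16% | 23.6% |
| 90% | 9% | 15.8% |
| 99% | 1% | 3.1% |

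The 25% is the maximum of p(1 − p), so it is a ceiling only for equality per SD. A simulation with 5,730 + 3,434 + 21,740 = 30,904 people and both interactions in one linear model, set near 50% CNS power, gave 27% (per SD) and 29% (per allele).

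**2. Testing the difference directly.** On the scale where equality holds, the contrast favours CNS 2.5% of the time (the upper tail of a 5% test). The simulated two-sided rates were 5.1% (per SD) and 6.1% (per allele), within simulation error of 5%.

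**3. If the scale is the wrong one.** At 50%, 80% and 99% CNS power:
- Per-SD contrast when equality is per allele, noncentrality (d − d/r)/√2: favours CNS 3.5%, 4.0% and 5.1% of the time.
- Per-allele contrast when equality is per SD, noncentrality (d − dr)/√(1 + r²): 1.7%, 1.4% and 1.1%.

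**4. If any of three diet scores may be used.** Taking three equally correlated normal contrasts, the 2.5% becomes 7.3%, 6.3%, 4.9% and 4.2% at correlations 0, 0.5, 0.8 and 0.9. With 0.05/3 for each it is 2.5%, 2.2%, 1.8% and 1.5%.

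**5. Power of the contrast.** Per SD, with equal standard errors and zero covariance, the noncentrality is d(1 − f)/√2, where f is the non-CNS interaction as a fraction of the CNS one. At 80% CNS power (d = 2.802):
- f = 0: 2.802/√2 = 1.981, power 51% (34% at 0.05/3).
- f = 0.5: 1.401/√2 = 0.991, power 17% (8% at 0.05/3).

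If the two product estimates correlate between −0.1 and 0.1, the 51% ranges from 47% to 55%.

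**The case against.** The strongest reply is that the error rates above belong to a rule the plan does not contain. Item 2 prespecifies both interactions and nowhere says that significance in one and not the other will count as support. That is right: the misreading is possible, not planned, and the percentages show only what it would cost. The plan nevertheless offers no other rule for deciding the clause.

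A second reply is that the document is brief throughout. Alpha, pooling and diet-score priority are unstated for every analysis, so those gaps are not particular to this clause. This also stands. The missing contrast and the missing common scale are what is specific here, and the contrast is enough for the point without the rest.

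Third, a contrast with 51% or 17% power will often be inconclusive, so the clause could simply be labelled descriptive, with both estimates and intervals shown on one scale. That would be honest, but it would leave a stated hypothesis untested. Low power for a difference argues for reporting its interval, not for inferring the difference from separate tests.

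Finally, the contrast's 2.5% requires valid standard errors. Diet was measured repeatedly in the NHS and HPFS, and item 2 does not mention within-person correlation. That is a separate question about item 2, which the contrast inherits.

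**Conclusion.** The concern holds. The second hypothesis makes a comparative claim, and no planned analysis tests the comparison or fixes the scale on which it would be made. This can be seen from the text alone and depends on no assumption.

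The size of the possible error does depend on assumptions. Under those listed, and only if the clause were read from the pattern of p-values, a false CNS-specific claim would arise in 1% to 25% of studies when the interactions are equal per SD, depending on power, against 2.5% for a direct contrast on the matching scale. At very high power the p-value pattern is no worse than the contrast in that case; the excess risk is at low to moderate power. Scale choice and free choice among diet scores matter less, moving the 2.5% to between 1.1% and 7.3% in the cases examined.

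Whether diet quality modifies the genetic association at all is still tested as planned. The point should be fixed, but it does not undermine the main analysis.

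**What to change.** Add to item 2:
- In each cohort, keep the item 2 model type and fit both scores together: BMI ~ diet + CNS + nonCNS + diet×CNS + diet×nonCNS. Any allowance for repeated records adopted for item 2 should carry over.
- Fix one common scale in advance, per allele or per SD, and report the other as a sensitivity analysis.
- Test the difference between the two product coefficients using their covariance. Combine the cohort contrasts by a stated method, such as inverse-variance meta-analysis, and report the difference with its confidence interval.
- Name one primary diet score for this contrast and treat the other two as supportive. AHEI is the natural candidate, since the first hypothesis and items 1 and 4 already use it. If all three are to count, adjust, for example 0.05/3 each.
- Base any CNS-specific statement on this contrast, and report a non-significant result as inconclusive. Keep the separate-score analyses as planned.

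The cost is a few sentences of plan text and one extra model per cohort and diet score, with no new data. The drawback is the contrast's lower power: a real CNS-specific difference would often remain unproven. The further loss at 0.05/3 is a reason to name one primary diet score.

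### The CNS-specific hypothesis cannot be read from separate diet interactions of a 54-SNP and a 43-SNP score with no common unit and no direct contrast

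*Combined protocol and SAP*

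**What the plan says.** The second bullet under Hypotheses is comparative. Better diet is expected to go with a "less pronounced association between genetic score and BMI, particularly the score of CNS SNPs". The Background gives a related aim, the "identification of subgroup of established SNPs whose association with BMI could be most significantly modified by diet".

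The second bullet under Exposure splits the 97 SNPs into "CNS SNP (54 SNPs) and non-CNS SNP (43 SNPs"). On construction it says only "Total, CNS, and non-CNS SNP scores will be calculated". It states no weights, no unit (per allele, per SD or per quantile) and no cut-points.

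Item 2 of Statistical analysis tests diet-by-score interactions on BMI, and "The genetic scores will include total SNP score, CNS SNP score, and non-CNS SNP score". Item 3 stratifies the genetic association by diet and the diet association by genetic score. Item 4 repeats the interaction analysis for single AHEI components. No item compares the CNS interaction with the non-CNS interaction. The documents give no SNP effect sizes and no variance explained by either score.

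**The concern.** A claim that one score is modified more than the other needs a scale on which the two can be compared, and a test of the difference. The plan has neither. As written, the CNS statement would rest on setting two separate coefficients or two p-values side by side.

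Those quantities mix two things: how far diet weakens the SNP effects, and how strongly the score predicts BMI in the first place. If diet acts identically on every SNP, the score that explains more BMI variance shows the larger per-SD interaction and the smaller expected p-value. A CNS-specific conclusion could then reflect how the SNPs were divided between the scores. Equally, a real CNS-specific effect could be hidden if the CNS score were the weaker one. Half of the second hypothesis is at stake, and with it the Background's argument for individualised prevention.

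**Working it through.** **Inputs from the documents.** 54 CNS and 43 non-CNS SNPs: 54 + 43 = 97, and 54/97 = 55.7%, consistent with the Background's statement that more than half are CNS-enriched. Participants: 5,730 + 3,434 + 21,740 = 30,904. The plan has no power or effect-size figure to reproduce.

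**Model.** Let diet quality D (in SD) weaken every SNP effect b_j by the same proportion c, so that BMI = sum(b_j G_j) × (1 − cD) + error. SNPs are taken as independent with similar allele frequencies p. Let r be the mean CNS effect divided by the mean non-CNS effect. Diet treats the two sets identically, so a fair comparison should show no difference.

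**Expected interaction on each scale**
- Per allele (unweighted count): −c × mean(b). CNS/non-CNS ratio = r.
- Effect-weighted score in predicted-BMI units: −c. Ratio = 1.
- Per SD (a quantile contrast behaves alike): −c × sqrt(sum 2p(1−p)b²). Ratio = r × sqrt(54/43).
- z statistic: proportional to the per-SD value on any of these scales. Ratio = r × sqrt(54/43).

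| r (assumed) | Per allele | BMI unit | Per SD, and z |
|---|---|---|---|
| 0.80 | 0.80 | 1.00 | 0.90 |
| 0.89 | 0.89 | 1.00 | 1.00 |
| 1.00 | 1.00 | 1.00 | 1.12 |
| 1.25 | 1.25 | 1.00 | 1.40 |
| 1.50 | 1.50 | 1.00 | 1.68 |

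Break-even is r = sqrt(43/54) = 0.89 for per-SD and z comparisons, and r = 1 per allele.

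A small simulation agrees in direction. It used 100 data sets per setting, 30,904 people, c = 0.10, residual SD 4.5 and a mean effect of 0.1 kg/m² per allele. The CNS score had the larger |z| in 33–39%, 61–62% and 70–71% of data sets at r = 0.8, 1.0 and 1.25. The BMI-unit coefficient ratio was 0.89, 1.05 and 1.03, which is 1.00 within simulation noise.

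**What this does to significance.** Illustrative assumptions, none in the documents: three cohorts pooled, BMI SD 4.5, total score R² 2.5%, c = 0.15 for every SNP. Then:
- SE of a per-SD by per-SD interaction = 4.5/sqrt(30,904) = 0.0256.
- Total-score slope per SD = sqrt(0.025) × 4.5 = 0.71. If CNS SNPs carry a share s of the explained variance, this divides into 0.71 × sqrt(s) and 0.71 × sqrt(1−s).
- z = 0.15 × slope / 0.0256. The chance that only the CNS score is significant is power(CNS) × [1 − power(non-CNS)]. At s = 56% that is 0.875 × (1 − 0.793) = 0.18.

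| CNS share s | z, CNS v non-CNS | Only CNS significant | Only non-CNS significant | SD-unit difference test rejects |
|---|---|---|---|---|
| 56% (equal effects) | 3.11 v 2.78 | 18% | 10% | 6% |
| 67% (illustrative) | 3.40 v 2.41 | 30% | 5% | 11% |
| 75% (illustrative) | 3.61 v 2.08 | 43% | 3% | 19% |

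The last column should be 5%. At s = 56%, changing c to 0.10 gives 30% v 21% for the two discordant patterns, and c = 0.05 gives 15% v 13%.

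**Precision of the proposed contrast.** In predicted-BMI units each interaction has SE 0.0256/slope. At s = 56% that is 0.0256/0.531 = 0.048 and 0.0256/0.474 = 0.054, so the difference has SE sqrt(0.048² + 0.054²) = 0.072. At s = 75% the SEs are 0.042 and 0.072, and the difference has SE 0.083. The gap detectable with 80% power is (1.96 + 0.84) × SE, about 20 to 23 percentage points. For 20% v 10% weakening, power is 23–28%.

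**The case against.** A reader might infer that the plan is biased towards finding a CNS effect, because CNS SNPs are more numerous and stronger. The documents support only the first half of that. They give counts, not effect sizes, so unequal strength is an assumption and the direction is not established: below r = 0.89 the non-CNS score would look more modified per SD. Nor does SNP number matter on every scale. With an unweighted allele count it drops out, and the ratio at equal strength is 1.00. For the same reason the total score need not look more modified than its parts per allele. The plan does not say which scale it will use.

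The effect that follows from the documented counts is also modest: 1.12 per SD and, on the assumptions above, 6% rejection instead of 5%. The larger figures need CNS variance shares of 67–75%, which have no source in the documents. Pooling to 30,904 is not stated either.

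Proportional weakening is one choice of estimand. The hypothesis speaks of a less pronounced association and does not say proportionally. A larger absolute change in kg/m² is also effect modification, and if diet lowered every SNP effect by the same absolute amount, a ratio would make the weaker score look more modified. Item 3 estimates genetic slopes within diet strata, so percent weakening could be worked out from it, although the plan does not commit to doing so.

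These points stand, and they limit the size and direction of the problem. They do not supply the missing unit or the missing contrast. Scale dependence is itself a reason to fix the scale in advance. Rescaling alone is also not enough: the two p-values still differ with the variance each score explains, so only a direct test answers the comparative question.

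**Conclusion.** The concern holds as a gap in specification. The CNS-specific part of the second hypothesis is not identified by the analyses listed, because separate interactions and their significance can differ when diet acts equally on all SNPs.

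From the documented counts plus equal SNP effects, the distortion is a factor of 1.12 for per-SD or p-value comparisons and none for per-allele or predicted-BMI coefficients. Beyond that, size and sign depend on relative SNP strength, which the documents do not give. The discordance percentages illustrate the mechanism under the stated assumptions and are not estimates for these cohorts. The documents do not show that the plan favours the CNS score, only that it cannot separate a CNS-specific effect from a difference in score strength. The change should be made, since half of a stated hypothesis depends on it and the data are already held.

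**What to change.** Amend the second bullet under Exposure and items 2 to 4 of Statistical analysis as follows.

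1. Build each score from BMI-raising alleles weighted by the per-allele effects of the plan's own source GWAS, and express both scores in the same predicted-BMI unit. State that unit, converting if the published effects are not in kg/m².
2. In each cohort, fit one model with both scores, diet quality and both diet-by-score interactions. If an overall statement is wanted, say how cohort results will be combined.
3. Prespecify a test of equality of the two interactions, with the confidence interval for their difference. Base the CNS v non-CNS statement on this, and say explicitly that one interaction being significant and the other not is no evidence of a difference.
4. As a supporting scale, report for each score the interaction divided by its main effect (percent weakening per SD of diet quality) with a bootstrap interval. On the assumptions above the main effects are large enough for a stable ratio: z about 21 and 18 at a 56% share, 24 and 14 at 75%.
5. Optionally, compare the observed contrast with those from random 54/43 splits of the 97 SNPs.

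The cost is some SAP wording and a short program, with no new data. The drawback is imprecision: an SE of about 7–8 percentage points for the difference in percent weakening, even with all three cohorts pooled. The plan should say so, and should treat a non-significant contrast as inconclusive rather than as evidence that the two SNP sets are modified alike.

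### Hypothesis 1 compares CNS with non-CNS SNPs on AHEI intakes, but no planned analysis makes that comparison

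*Combined protocol and SAP*

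**What the plan says.** The first bullet under Hypotheses is a between-class claim: CNS SNPs "were more likely to be associated with food and nutrient intakes featured in AHEI in comparison to SNPs enriched in other tissues". The Exposure section fixes the classes, 54 CNS and 43 non-CNS SNPs out of 97.

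The Statistical analysis section has four items.

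- Item 1: "The associations of individual SNP with AHEI components at baseline will be examined using linear regression and the results will be presented in Heatmap".
- Item 2: "The interactions between diet quality scores and genetic scores in relation to BMI will be examined". It adds: "The genetic scores will include total SNP score, CNS SNP score, and non-CNS SNP score".
- Item 3 has two stratified analyses, of which the first reads "the association of diet quality score with BMI will be stratified by genetic score". The second exchanges the roles of diet and genes and keeps BMI as the outcome.
- Item 4: "The interactions between AHEI components and genetic scores in relation to BMI will be examined".

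The Outcome section names one outcome: "BMI measured after diet assessment with 2-year lag in the NHS and the HPFS and 3-year lag in the WGHS".

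**The concern.** A claim that one class of SNPs is associated with diet more often than another needs a contrast of the two classes with diet as the outcome. Item 1 has diet as the outcome but does not mention the classes, a contrast between them, or a rule for calling a SNP associated. The items that use the CNS and non-CNS scores have BMI as the outcome.

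At stake is how Hypothesis 1 would be judged. A heatmap gives neither the size of the class difference nor its uncertainty. With no rule fixed in advance, the way of comparing the classes would be chosen after the colours are seen.

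**Working it through.** **Hypotheses against analyses.** The plan gives no power figure or significance level for this point, so there is nothing to reproduce. The check is a reading of the items side by side.

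| Item | Outcome | Genetic unit | CNS vs non-CNS contrast on intake? |
|---|---|---|---|
| 1 | AHEI components | single SNP | No |
| 2 | BMI | total, CNS and non-CNS scores | No |
| 3 | BMI | genetic score | No |
| 4 | BMI; AHEI components enter as interaction terms | genetic scores | No |

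The partition itself is consistent: 54 + 43 = 97.

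**Can the heatmap be read by eye?** Two illustrations, with inputs that are assumptions and not in the documents:

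- Suppose 10 components. Item 1 then has 97 × 10 = 970 regressions. At an unadjusted 5% level and with no true association, 0.05 × 970 = 48.5 cells would be flagged on average: 0.05 × 540 = 27.0 in CNS rows and 0.05 × 430 = 21.5 in non-CNS rows.
- Suppose each SNP has the same chance p of being called associated, whatever its class. With X ~ Bin(54, p) and Y ~ Bin(43, p), P(X > Y) = 0.51, 0.58 and 0.67 for p = 0.05, 0.10 and 0.20. The CNS class tends to show the larger count simply because it has more SNPs. The larger proportion falls to CNS about half the time (0.49 to 0.50).

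So a comparison should use proportions, and it should carry its uncertainty.

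**How much could 54 against 43 SNPs show?** Suppose each SNP's true status were known. The standard error of the difference is √[p₁(1−p₁)/54 + p₂(1−p₂)/43].

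- 20% vs 10%: √(0.16/54 + 0.09/43) = 0.071. The 95% half-width is 1.96 × 0.071 = 14 points, for a difference of 10. Two-sided 5% power is 0.26.
- 30% vs 10%: √(0.21/54 + 0.09/43) = 0.077. The half-width is 15 points, for a difference of 20. Power is 0.68.
- Fisher's exact test needs a difference of 14 to 29 points for 80% power as the non-CNS share runs from 0 to 30%.

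**Which statistic matches the hypothesis?** Two were simulated with label permutation. Assumptions: mostly 9 components (9 or 11 in some runs), within-SNP correlation 0 to 0.5, and one or three components affected per associated SNP, with mean z of 3 or 4.5.

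| Setting | Mean z-squared per SNP | Share of SNPs called associated |
|---|---|---|
| Equal 20% shares, mean z 4.5 (CNS) vs 3 (non-CNS): rejection | 16–31% | 4–10%; up to about 12% when rerun |
| 30% vs 10%: power | 0.16–0.66 | 0.25–0.55; similar when rerun |
| 30% vs 10%, three components, one non-CNS SNP with z raised by 8: power | 0.003 or 0.16 | 0.35–0.44 |

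The share is closer to what the hypothesis says and far less exposed to a single SNP, but it is not immune to effect size. With 9 components the per-component level is 0.05/9, so the cut-off is |z| > 2.77. If one component is affected and components are independent:

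- An unassociated SNP is called with probability 1 − (1 − 0.05/9)⁹ = 0.049.
- A SNP with mean z 3 is called with probability about 0.61, and with mean z 4.5 about 0.96.
- At equal true shares of 20%, the expected called shares are 0.2 × 0.96 + 0.8 × 0.049 = 0.23 and 0.2 × 0.61 + 0.8 × 0.049 = 0.16. That is a 7-point gap with no difference in true share.

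**The case against.** The strongest defence is that item 1 is descriptive: it supplies all the estimates, and a reader can compare the classes on the heatmap. It stands in part. The regressions do contain what a comparison needs, and a purely descriptive aim would be legitimate. But the plan does not say that the heatmap is grouped by class, and it lists the claim as a hypothesis beside Hypothesis 2. A display of single SNPs does not become a class comparison unless someone specifies one.

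A second objection is that a reviewer should not dictate a test. That also stands in part. The gap does not depend on which test is chosen, and the proposal below is an example. Average z-squared per SNP may look like the natural summary, but it mixes how many SNPs are associated with how strong the signals are. It therefore does not by itself answer the hypothesis as worded.

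A third objection is that pooling the cohorts would be a new decision. That is correct. The plan states no pooling, and WGHS has 21,740 of 5,730 + 3,434 + 21,740 = 30,904 participants (70%), so it would probably dominate a combined estimate.

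A reader might also infer that the gap undermines the BMI results, or that the heatmap is biased toward the hypothesis. The documents support neither. Items 2 to 4 do not depend on item 1, and the tilt toward CNS appears in raw counts, not in proportions.

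**Conclusion.** The gap is real and visible in the text: one of two stated hypotheses has no estimate and no test. This rests on the wording alone and on none of the assumed figures above.

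The change should be made, but it is a cheap improvement rather than a condition for the study. Hypothesis 1 supports the main question, which concerns BMI and has its own analyses.

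The documents do not support saying that Hypothesis 1 cannot be tested, since the planned regressions suffice. Nor do they support promising that the added test would settle it. Power is limited and depends on the number of components, their correlation and the strength of the associations, none of which the documents give. No single detectable difference should be written into the plan.

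**What to change.** Add to item 1 one pre-specified between-class comparison with the SNP as the unit and an estimand that matches the hypothesis. For example:

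1. Call a SNP associated if its smallest p-value over the AHEI components passes a threshold corrected for the number of components.
2. Report the proportion associated in CNS minus that in non-CNS SNPs, with a 95% interval.
3. Obtain the p-value by permuting the class labels over the 97 SNPs, keeping each SNP's row of components intact.
4. State in advance whether this is done per cohort or on estimates combined across the three cohorts.
5. State that a non-significant result would not refute the hypothesis.

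Keep the heatmap as the display, with rows grouped by class. Mean z-squared may be a secondary summary only, labelled as strength of evidence, because it also responds to effect size, allele frequency and single outlying SNPs.

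If item 1 is meant as description only, reword Hypothesis 1 as descriptive and draw no conclusion on the class difference.

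Cost: a few lines of plan text, a short analysis of output already planned, and one decision on combining cohorts. No new data are needed. The downsides are that the proportion depends on the chosen threshold and, through it, partly on effect size, and that the question may stay unresolved with 97 SNPs.

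### The genetic score by diet interactions in items 2 and 4 can pick up part of a correlated behaviour's effect modification, and adjusting for that behaviour as a main effect would not remove it

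*Combined protocol and SAP*

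**What the plan says.** The title describes the work as "Results From Three Observational Studies", so participants chose their own diets. The second hypothesis reads "Higher diet quality was related with less pronounced association between genetic score and BMI, particularly the score of CNS SNPs". With the genetic score coded so that higher values mean higher BMI, this predicts a negative genetic score × diet coefficient.

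Item 2 of Statistical analysis tests it: "The interactions between diet quality scores and genetic scores in relation to BMI will be examined using generalized linear model". Item 4 repeats the approach for components: "The interactions between AHEI components and genetic scores in relation to BMI will be examined using generalized linear model". Both use linear regression in the WGHS. Item 3 stratifies the genetic association by diet score and the diet association by genetic score. None of the three items names a covariate, either as a main effect or as a product with the genetic score, and no sensitivity analysis addresses other modifiers.

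The Background gives the intended reading. It says "However, it is not known whether diet quality could modify the genetic association with BMI" and expects that finding the SNPs whose association is "most significantly modified by diet will provide evidence to individualized obesity prevention".

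**The concern.** People with better diets may also differ in physical activity, smoking and age. Confounding of an interaction differs from confounding of a main effect. What matters is whether one of these characteristics also changes the slope of BMI on the genetic score. If it does, and it is correlated with diet quality, the diet interaction carries part of that change.

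This is more than a missing covariate list. The usual way to complete a short plan is to add such variables as main effects, and that would not cure the problem. Only products of the genetic score with those variables address it.

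At stake is the attribution to diet. If a behaviour accompanies better diet and weakens the genetic effect, the spurious term is negative and favours hypothesis 2. A larger sample does not shrink it. Lagging BMI behind diet does not help either, because the behaviours are present when diet is assessed.

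**Working it through.** The plan states no power, alpha or effect-size figure, so there is none to reproduce.

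**Inputs from the documents.** Study Population gives 5,730 (NHS), 3,434 (HPFS) and 21,740 (WGHS).

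**Assumptions, not in the documents.** Two-sided alpha 0.05; residual SD 4.5 kg/m²; one record per person; genetic score G, diet D and behaviour A standardised and jointly normal; G independent of D and A; corr(D, A) = r from 0.2 to 0.3; A changes the genetic slope by gamma, from -0.1 to -0.2 kg/m² per SD; no true diet modification.

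**Step 1: the bias.** Let BMI = b0 + bG·G + bD·D + bA·A + gamma·G·A + error. Because A = r·D + (a part unrelated to D), G·A = r·G·D + (a part unrelated to G·D). Without G·A in the model, the G·D coefficient tends to r × gamma. G·D is uncorrelated with A itself, so adding A alone changes nothing. Adding G·A takes the limit to zero.

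- Small end: 0.2 × (-0.1) = -0.02 kg/m² per SD × SD.
- Large end: 0.3 × (-0.2) = -0.06.

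**Step 2: false rejection.** SE ≈ 4.5/√n and m = |bias|/SE. The rejection probability is Φ(m − 1.96) + Φ(−m − 1.96).

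| Cohort | n | SE | m, small to large | Rejection |
|---|---|---|---|---|
| HPFS | 3,434 | 0.0768 | 0.26 to 0.78 | 6% to 12% |
| NHS | 5,730 | 0.0594 | 0.34 to 1.01 | 6% to 17% |
| WGHS | 21,740 | 0.0305 | 0.66 to 1.97 | 10% to 50% |

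With r = 0 or gamma = 0 the bias is zero and rejection is 5%.

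**Step 3: simulation check.** Data were generated as BMI = 25.5 + 0.6G − 0.3D − 0.6A + gamma·G·A + N(0, 4.5), with n = 21,740, r = 0.3, gamma = -0.2 and 600 replicates.

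| Model | Mean G × D | SE | Rejection |
|---|---|---|---|
| No adjustment | -0.060 | 0.0308 | 47.8% |
| A as main effect | -0.060 | 0.0306 | 47.7% |
| A and G × A | 0.000 | 0.0320 | 4.5% |

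**Step 4: precision cost.** With G·A in the model the SE grows by 1/√(1 − r²): 1.021 at r = 0.2 and 1.048 at r = 0.3, or about 2–5%.

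**Step 5: measurement error in A.** If A is recorded with reliability L, the fraction of the bias left after adding the product term is (1 − L)/(1 − L·r²). At r = 0.3:

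- L = 0.7: 0.30/0.937 = 0.32, leaving 0.32 × (-0.06) ≈ -0.019.
- L = 0.5: 0.50/0.955 = 0.52, leaving 0.52 × (-0.06) ≈ -0.031.

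So about a third to a half remains at these reliabilities.

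**The case against.** **The size is assumed.** This stands. The documents give no diet–behaviour correlation, no gene–behaviour interaction and no BMI SD. Against the simulated main genetic slope of 0.6, gamma = -0.2 is large, so the upper figures are the unfavourable end. The mechanism is certain given its premises, but whether a material bias exists here cannot be known from the plan.

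**Hypothesis 2 is worded as an association.** This stands in part. As a description of how the genetic slope varies with diet, the coefficient is valid. The difficulty arises when it is read as modification by diet, which is how the Background frames the question and its use.

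**Direction is conditional.** This stands. A negative bias requires a behaviour that both accompanies better diet and weakens the genetic effect. Nothing in the documents gives the sign for physical activity, smoking or age, and several modifiers could offset one another.

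**Stronger readings that the documents do not support.**

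- A reader might infer that the plan credits diet with all of a behaviour's modification. Only the share r carries over, 20–30% under these assumptions.
- A reader might infer that false support is likely in every cohort. In the NHS and HPFS the inflation is modest even at the large end.
- A reader might apply the calculation to the summed 30,904 participants (5,730 + 3,434 + 21,740). The plan states no pooling or meta-analysis.
- A reader might infer that product terms remove the problem. They do so only for behaviours that are included and measured without error.

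**Conclusion.** The concern holds in a limited form. As written, the items 2 and 4 interactions cannot separate modification by diet from modification by a behaviour correlated with it, and main-effect adjustment would not separate them. The expected spurious coefficient is r × gamma, or -0.02 to -0.06 kg/m² per SD × SD under the stated assumptions. That matters most in the WGHS, where the standard error is smallest.

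The calculation treats each person as contributing one record. The NHS and HPFS measured diet repeatedly, and any precision gained from repeated records would raise their rejection figures somewhat. The plan remains usable. What needs support from a further model is the attribution of modification to diet quality itself.

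**What to change.** 1. **Second model.** For items 2 and 4, pre-specify a second model in each cohort. Add the main effects of age, physical activity and smoking, measured at or before the diet assessment, and the product of each with the same genetic score used in the diet interaction.
2. **Reporting.** Give the diet interaction estimate and 95% CI from the planned and second models side by side, for each cohort.
3. **Attribution rule.** Attribute modification to diet quality itself only if the second-model CI excludes zero in the hypothesised direction. Otherwise describe the finding as an association that may reflect a healthy-lifestyle pattern. A CI that includes zero in a smaller cohort may reflect imprecision and should not be read as proof that diet plays no part.
4. **Item 3.** Keep the stratified analysis and report slopes from the second model as a supplement.
5. **Limitation.** State that the added terms reduce the bias but do not eliminate it when behaviours are measured with error or left out.

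The cost is three main effects and three product terms per model, and an interaction standard error about 2–5% larger. No new participants are needed. No new data are needed either if the cohort files hold these variables, which is an assumption because the documents do not list them.
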